## **SAMPLE SIZE**

No formal sample size calculations were performed for the study. It is estimated that with 225 subjects enrolled with age 18-35, a 12-month Pearl Index of 0.6 (1 observed pregnancy), and 2,015 evaluable cycles, we will observe a 95% confidence interval for the 12-month Pearl Index of (0.1, 3.3).

2,015 evaluable cycles assumes that in the overall study:

- Each subject will average 10 evaluable cycles of LevoCept use
- 1% of subjects will not provide any e-diary data and will be excluded from the primary efficacy population
- Subjects will not have intercourse or will use backup contraception in 9.2% of cycles

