## INVESTIGATIONAL PLAN SUMMARY

Title:	Evaluation of the Effectiveness, Safety and Tolerability of LevoCept (Levonorgestrel-Releasing Intrauterine System) for Long-Acting Reversible Contraception
Protocol #:	CMDOC-0022 Version 4.0 / 18 October 2017
Device Name:	LevoCept Intrauterine Contraceptive; Levonorgestrel-Releasing Intrauterine System (referred to as LevoCept or Study Device throughout this document)
Study Design:	Prospective, multi-center, single-arm, open-label, Phase II clinical study
Study Purpose:	To evaluate the effectiveness, device placement, safety, and tolerability of LevoCept to support commencing a Phase III Clinical Study
Study Duration:	Subject enrollment will take approximately 5 months. Each subject will be followed for 12 months after device placement for the protocol endpoints, and then every 6 months thereafter for up to 24 additional months for those subjects who wish to continue study device use.
Enrollment:	Up to 250 subjects will be consented, screened and have LevoCept placed, with a goal to have 2240 evaluable cycles at 12 months. It is planned that 225 of the 250 subjects will be within the 18-35 year age range, with a total of 2015 evaluable cycles. The remaining 25 subjects will be within the 36-40 year age range.
Investigational Site Information:	This study will be conducted at approximately 16 centers in the U.S.
Follow-up:	
Physical assessment (office visit) will occur at weeks 6, 13, 26 and 52 after placement, with monthly contact. For those subjects who wish to continue study device use after 12 months, follow-up office visits will occur every 6 months with contact at the end of each 28-day cycle beginning after the 52-week visit. Additional visits will be conducted if necessary for safety issues.
 
Follow-up after early study device removal:
 
Subjects requesting LevoCept removal to become pregnant will be followed for either; six (6) months, until they decide to no longer try to conceive or they become pregnant, whichever comes first. All subjects in whom LevoCept is removed, for any reason, will be required to use an alternative contraceptive for the first two weeks following removal. Hormonal contraceptive pills will be reimbursed by the sponsor as a contraceptive option during this

time unless the subject has a MEC category 4 condition precluding their use.

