## **20.6 Primary Outcome**

The primary outcome measure is effectiveness and will be evaluated as absence of pregnancy during LevoCept use. Pregnancies judged to have occurred while a study device was in place (determined by ultrasound and medical assessments) will be included in the analysis of pregnancies.

For the primary evaluation of effectiveness, the Pearl index (and 95% confidence intervals) will be calculated in subjects aged 18-35 at the time of LevoCept placement through the date of LevoCept removal or pregnancy, excluding the following (unless the subject became pregnant in the cycle):

- Cycles where back-up contraception use was reported by the patient
- Cycles with no intercourse.
- Cycles in which emergency contraception was used

The Pearl Index is based on 28-day cycles and defined as the number of pregnancies per 100 woman-years (with one year comprising 13 28-day cycles). The cycle is defined as 28 days with the day of LevoCept placement as cycle 1

day 1. Pearl index will be summarized annually for each of the 3 years and cumulatively.

The EP population will be used for the primary evaluation of effectiveness.

Life table (Kaplan-Meier method) analyses will be used as further assessment of pregnancies. Pregnancy rate will also be summarized annually for each of the 3 years and cumulatively.

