3.2 Study Sample Size

No formal sample size calculations were performed for the study. It is estimated that with 225 subjects enrolled with ages 18-35, a 12-month (13 cycles) Pearl Index of 0.6 (1 observed pregnancy), and 2,015 evaluable cycles, we will observe a 95% confidence interval (CI) for the 12-month Pearl Index of (0.1, 3.3).

4 Primary Efficacy and Safety Variables

For all change from baseline variables, baseline is defined as the last non-missing value on or before the day of study device successful placement. Change from baseline to post-baseline will be calculated as the post-baseline value minus the baseline value. If either the baseline or post-baseline value is missing for a particular variable, change from baseline will be missing.

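### The 95% CI of (0.1, 3.3) given for 1 pregnancy in 2,015 cycles does not reproduce: exact Poisson gives (0.02, 3.6), Wilson (0.1, 3.6)

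*Protocol*

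**What the plan says.** Both documents state that no formal sample size calculation was done. In its place they give one illustration for women aged 18-35. The protocol's Sample Size paragraph takes a Pearl Index of 0.6, from one pregnancy, and says that with "2,015 evaluable cycles, we will observe a 95% confidence interval for the 12-month Pearl Index of (0.1, 3.3". SAP 3.2 gives the same result: "we will observe a 95% confidence interval (CI) for the 12-month Pearl Index of (0.1, 3.3".

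Two cycle totals appear in the plan. The Enrollment row of the protocol's Investigational Plan Summary describes up to 250 subjects "with a goal to have 2240 evaluable cycles at 12 months", and then says that "225 of the 250 subjects will be within the 18-35 year age range, with a total of 2015 evaluable cycles". The primary effectiveness analysis is limited to ages 18-35 (Protocol 20.1 and 20.6; SAP 5.5), so 2,015 is the relevant denominator.

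Protocol 20.6 fixes the scale: the Pearl Index is "defined as the number of pregnancies per 100 woman-years (with one year comprising 13 28-day cycles". SAP 4.1 writes this as pregnancies times 1300 divided by cycles at risk.

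Protocol 20.6 asks for 95% confidence intervals and the SAP Table 14.2.1 layout has a column for them, but neither says how they are computed. The SAP text available for this review runs from 6.2.6 directly to 6.2.9, so a method may be named in text that could not be seen.

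**The concern.** The interval is offered as what the 18-35 group will deliver. All of its inputs are printed, so it can be checked directly, and the common exact and score-type methods give a higher upper limit than 3.3. The figure tells a reader how tightly this Phase II study will bound the pregnancy rate before Phase III begins. If the upper limit is too low, the plan promises slightly more precision than 2,015 cycles can give, and the SAP carries the error forward.

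**Working it through.** **Inputs.** x = 1 pregnancy and L = 2,015 cycles (Protocol Sample Size; SAP 3.2); 1300 per cycle as the scale (SAP 4.1); 95%, taken as two-sided, so z = 1.96.

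**Point estimate.** 1 × 1300 / 2015 = 0.645, printed as 0.6. This reproduces.

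**Cycle count.** The Sample Size assumptions are 10 cycles per subject, 1% without diary data and 9.2% of cycles excluded. 225 × 10 × 0.99 × 0.908 = 2,023, against 2,015 printed. For 250 subjects the same product is 2,247, against 2,240. These agree closely, and using 2,023 would still give an upper limit of 3.58 (exact) or 3.64 (score).

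**Interval at 2,015 cycles.** The multiplier is 1300/2015 = 0.6452.

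- Exact Poisson: the limits for a count of 1 are χ²(0.025; 2 df)/2 = 0.0253 and χ²(0.975; 4 df)/2 = 5.572. Multiplied by 0.6452: (0.016, 3.595).
- Poisson score: x + z²/2 ± z√(x + z²/4) = 2.921 ± 2.744, that is 0.1765 and 5.665. Multiplied by 0.6452: (0.114, 3.655).
- Wilson on cycles, with p = 1/2015 and limits multiplied by 1300: (0.114, 3.648).

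| 95% method | 2,015 cycles | 2,240 cycles |
|---|---|---|
| Exact Poisson | 0.016, 3.595 | 0.015, 3.234 |
| Poisson score | 0.114, 3.655 | 0.102, 3.288 |
| Wilson on cycles | 0.114, 3.648 | 0.102, 3.282 |
| Wilson on woman-years (L/13) | 0.114, 3.564 | 0.103, 3.214 |
| Jeffreys (binomial, cycles) | 0.070, 3.012 | 0.063, 2.710 |

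Also at 2,015 cycles, mid-P gives (0.03, 3.18) and log-Wald (0.09, 4.58). Clopper-Pearson, Agresti-Coull, likelihood-ratio, Byar, Wald, square-root and continuity-corrected score intervals were tried as well. None of the 95% methods prints as (0.1, 3.3) from 1 in 2,015. Rounding of L does not explain the gap: the upper limit prints as 3.3 only for about 2,198 to 2,266 cycles (score) or 2,162 to 2,229 (exact).

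**Routes that do print as (0.1, 3.3).**

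- Score or Wilson on 2,240 cycles: (0.102, 3.288) or (0.102, 3.282). The Pearl Index there is 1300/2240 = 0.58, which also prints as 0.6.
- Wilson on the rounded Pearl Index: 1/0.006 = 166.7 woman-years gives (0.106, 3.320).
- Wilson on woman-years at 2,015 cycles, rescaled to 0.6: 3.564 × 0.6/0.645 = 3.31, with lower limit 0.106.
- Gamma(x+1) limits times the rounded 0.6: (0.145, 3.343).
- A 90% log-Wald interval at 2,015 cycles: (0.125, 3.342).

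**Size of the gap.** 3.595 − 3.3 = 0.295 (exact) and 3.655 − 3.3 = 0.355 (score), or 9% and 11% above the printed limit.

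**The case against.** The strongest objection is that, without a named method, there is no single correct upper limit. At 2,015 cycles Jeffreys and mid-P give 3.0 and 3.2, both below 3.3. That stands, and it limits the claim: the printed figure overstates precision relative to exact and score-type methods, not relative to every defensible one. It does not rescue the figure, since neither method gives (0.1, 3.3) either.

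The lower limit needs the same care. Under score or Wilson 0.1 is right; under exact Poisson it should be 0.02. Calling it an error would assume a method that the plan has not chosen.

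The match at 2,240 cycles may lead a reader to infer that the interval was computed on the whole 18-40 sample, and so describes a population that the primary analysis excludes. The documents do not support that conclusion. Both tie the interval to 225 subjects aged 18-35 and 2,015 cycles. The match needs a score or Wilson method, since exact Poisson at 2,240 prints as (0.0, 3.2), and working from the rounded 0.6 reaches the same figure without the older women.

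Finally, the interval is an illustration. The plan sets no hypothesis and no limit that the Pearl Index must stay under, and the reported interval will come from observed data. That also stands and lowers the severity.

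**Conclusion.** The printed interval is wrong as written: (0.1, 3.3) does not follow from 1 pregnancy in 2,015 evaluable cycles by any standard 95% method tried. With exact Poisson, Poisson score or Wilson on cycles, the upper limit is 3.6 to 3.7. This rests on a two-sided 95% level, on the 13-cycle year, and on taking the count and cycles as printed. The origin of the figure remains open.

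Severity is minor to moderate. It is the plan's only precision statement for its primary outcome and it appears in both documents, but no decision or enrolment number depends on it. A reader might take the error to mean that the trial is undersized; the plan sets no precision target against which that could be judged.

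**What to change.** In the protocol's Sample Size paragraph and SAP 3.2, recompute the interval from 1 pregnancy in 2,015 cycles with the unrounded Pearl Index, and name the method. Either exact Poisson, (0.02, 3.6), or Wilson on cycles, (0.1, 3.6), would do.

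Preferably use the same method for SAP Table 14.2.1 and say so there, so that planned and reported precision are comparable. If the SAP already names a method in text not seen here, the planning figure should follow it. Table 14.2.1 splits by parity and BMI, so cells with no pregnancies are likely and the method must handle them. Exact Poisson does: with none in 2,015 cycles the two-sided 95% upper limit is 3.689 × 0.6452 = 2.4. Exact Poisson is a suggestion; the documents do not require it.

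The cost is a few sentences and a slightly less favourable stated figure. Enrolment, visits and data collection are unaffected.

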## ABBREVIATIONS AND DEFINITIONS OF TERMS

AE	Adverse Event
BMI	Body Mass Index
BP	Blood Pressure
BUN	Blood Urea Nitrogen
BV	Bacterial Vaginosis
C	Celsius
CBC	Complete Blood Count
CCTN	Contraceptive Clinical Trials Network
CFR	Code of Federal Regulations
cm	Centimeters
CRF	Case report forms
Cu	Copper
CVR	Contraceptive vaginal ring
d	Day
DHHS	Department of Health and Human Services
dL	Deciliter
DSMB	Data Safety Monitoring Board
EC	Emergency contraception
eCRF	Electronic case report form
EDC	Electronic data capture
ECYC	Evaluable for Cycle Control
EE	Efficacy Evaluable
EMR	Electronic medical records
ENDTX	End of treatment
EP	Evaluable for Pregnancy
F	Fahrenheit
FDA	Food and Drug Administration
FSH	Follicle Stimulating Hormone
g	Gram
GCP	Good Clinical Practices
GnRH	Gonadotropin-Releasing Hormone
hCG	Human Chorionic Gonadotropin
HD	Health Decisions
HPV	Human Papillomavirus
ICH	International Conference on Harmonization
IEC	Independent Ethics Committee
IND	Investigational New Drug
IRB	Institutional Review Board
ITT	Intent-To-Treat
IUD	Intrauterine Device
kg	Kilograms
L	Liter
LTFU	Lost to follow up
MedDRA	Medical dictionary for regulatory activities
MITT	Modified Intent to Treat
mg	Milligrams
mL	Milliliter
mm	Millimeter
NDA	New Drug Application
NIH	National Institutes of Health
N/A	Not Applicable
OC	Oral Contraceptive(s)
Pap Test	Papanicolaou Test
SAE	Serious Adverse Event
SAP	Statistical Analysis Plan

SAS	Statistical Analysis Software
SCCC	Statistical and Clinical Coordinating Center
SCRN	Screening
SD	Standard Deviation
SOP	Standard Operating Procedure
STD	Sexually Transmitted Diseases
TVUS	Transvaginal ultrasound
UNS	Unscheduled
US	United States
V	Visit
X	Times
WHO	World Health Organization
:	To
/	Per
%	Percent
<	Less than
>	Greater than
≤	Less than or equal to
≥	Greater than or equal to
°	Degrees
±	Plus or minus
+	Plus

## 1. INTRODUCTION

The LevoCept Intrauterine Contraceptive is designed as a birth control device. There are over 61 million US women in their child-bearing years, ages 15 to 44. Thirty-eight million (38M) use some form of contraception (62%). Thirty-one (31%) percent do not use or need contraception because they are either trying to get pregnant, are pregnant, are infertile or are not sexually active. Seven (7%) percent are at risk for unintended pregnancy since they are using no method.

Contraceptive options for those 38 million US women include permanent sterilization (tubal ligation or vasectomy in male partner), contraceptive implants, intrauterine devices, injections, pills, patches, vaginal rings, male and female condoms, other female barrier methods, vaginal spermicides, and behavioral methods such as coitus interruptus and fertility awareness. Of all these methods, oral contraceptives are used by 30% of sexually active women. The more effective methods, such as intrauterine contraceptives, are used by fewer than 10.3% of women and long acting reversible contraception (LARC) 11.6%. The contraceptive CHOICE project showed that the pill failure rate is over 25 times higher than levonorgestrel-releasing contraception.

Intrauterine contraceptives have high initial costs, so early discontinuation rates have profound impacts on their cost-effectiveness. The early rates of user dissatisfaction due to complications or side effects may be associated with the materials used in these devices and/or their design. The Copper T380A IUD has been associated with complaints of increased bleeding, inter-menstrual bleeding and cramping pain. The 52mg LNG-IUS (Mirena®) is also associated with early complaints of irregular bleeding patterns, cramping pelvic pain and with amenorrhea.

With high-unintended pregnancy rates in the U.S. (45%), additional effective, safe and long-acting reversible contraceptives are needed. An intrauterine device with levonorgestrel that achieves high contraceptive effectiveness and has improved mechanical advantages could offer an attractive option to women seeking effective protection against unintended pregnancy. We believe the LevoCept Intrauterine Contraceptive embodies these advantages.

## 2. STUDY DURATION

Subject enrollment will take approximately 5 months. Each subject will be followed for 12 months after device placement for the protocol endpoints, and then every 6 months thereafter for up to 24 additional months for those subjects who wish to continue study device use.

---

Alan Guttmacher Institute Fact Sheets Oct 2013 ([www.guttmacher.org](http://www.guttmacher.org)): <https://www.guttmacher.org/fact-sheet/contraceptive-use-united-states#1>

[Changes in Use of Long-Acting Reversible Contraceptive Methods Among U.S. Women, 2009-2012.](#) Kavanaugh ML, Jerman J, Finer LB.

Obstet Gynecol. 2015 Nov;126(5):917-27. doi: 10.1097/AOG.0000000000001094. PMID: 26444110

accessed August 11, 2014.

### 3. INVESTIGATIONAL PRODUCT DESCRIPTION

The LevoCept Intrauterine Contraceptive is designed for use as a birth control method. The study device consists of a shape memory Nitinol spring with a stem-mounted levonorgestrel-releasing silicone reservoir and small tantalum sleeves at both distal arms for mechanical stability. A monofilament polymer Retrieval Thread is secured at the bottom of the frame.

The study device is shaped such that upon placement in the uterus, the Nitinol spring positions itself at the fundus, with the sleeved arms near the ostia of the fallopian tubes and the levonorgestrel-releasing reservoir in the center of the uterine cavity.

Figure 1 illustrates the basic design and layout of the study device.

[figure not shown]

Figure 1 – Design and layout of LevoCept

LevoCept contains 52 mg of Levonorgestrel, which releases at a rate of 20 micrograms per day. The study device is placed using a simple one-step introducer containing the preloaded and sterile study device. It is retrieved with the standard monofilament polypropylene retrieval thread.

Figure 2a shows the study device in its pre-loaded state (directly from the package) in the distal end of the introducer. Figure 2b shows a schematic of the study device oriented in the uterus post placement.

[figure not shown]

Figure 2 – (a) LevoCept in pre-loaded state (b) orientation in the uterus post placement

#### 4. STUDY TREATMENTS

After the risks and benefits of study participation have been explained to the candidate, her questions have been answered, she has signed a written consent and PHI form, and eligibility has been established, a subject identification number will be assigned by the Study Sponsor or designee. If the subject has a current IUD and pain is present from removal of the IUD, you should wait until the pain has resolved before insertion of LevoCept. If pain is present with the subject's current IUD, the subject should not be enrolled.

##### 4.1 LevoCept Insertion Timing

The following must be followed prior to LevoCept insertion to insure adequate contraception coverage:

##### 4.1.1 Subjects Using Any Hormonal Birth Control Method

Subjects using any hormonal birth control method can have LevoCept placed on any day of the menstrual cycle. If the insertion occurs in the first 7 days of the cycle, the hormonal contraception can be discontinued after insertion. If the insertion occurs after the first 7 days of the menstrual cycle, the subject should continue using hormonal contraception for an additional 7 days.

- Subjects using an implant (Implanon/Nexplanon) who have regular cycles, LevoCept should be inserted within seven days of onset of menses and the implant may be removed the same day.
- Subjects using an implant (Implanon/Nexplanon) who have irregular cycles or amenorrhea, LevoCept should be inserted and the implant should be removed seven days after IUD inserted
- Subjects using an implant (Implanon/Nexplanon) with regular cycles but who are beyond seven days of menses, LevoCept may be inserted but removal of implant should occur after seven days.

- Subjects using levonorgestrel IUD can have IUD removed and LevoCept placed on the same day. Insertion can occur on any day of the cycle.

#### **4.1.2 Subjects NOT Using Any Hormonal Birth Control Method (includes copper IUDs)**

Subjects NOT using hormonal contraception (including those currently using a copper IUD) must have the IUD inserted in the first 7 days of the menstrual cycle. Removal of a copper IUD and insertion of LevoCept may occur on the same day as long as the procedure is performed within the first 7 days of the menstrual cycle.

#### **4.2 LevoCept Intrauterine Contraceptive (Dosage and Formulation)**

LevoCept contains 52 mg of Levonorgestrel which is released at a rate of 20 micrograms per day. A single LevoCept design and dosage will be used in this study. LevoCept will be supplied by ContraMed, LLC. For further details, see the LevoCept Investigator's Brochure.

#### **4.3 LevoCept Supply and Administration**

Each LevoCept is preloaded in the inserter and packaged as a single use sterile system. Subjects will have LevoCept placed on "Day 1" of the trial. LevoCept should be stored in its sterile sealed package until study device placement.

See the Investigator's Brochure for a more detailed LevoCept product description, and the LevoCept instructions (e.g. Clinician's Quick Use Guide) for placement and removal instructions.

#### **4.4 LevoCept Storage and Accountability**

LevoCept should be stored at 25°C (77°F), with excursions permitted between 15°C to 30°C (59°F to 86°F) [See USP Controlled Room Temperature].

Study Device accountability, reconciliation and record maintenance are responsibilities that must be performed by the study site in accordance with all applicable regulatory requirements. Please refer to **Appendix 1**, Investigator Responsibilities for a detailed list of Investigator Responsibilities. All unused Study Devices will be stored for inventory and collection. Shipping procedures to return unused Study Devices are detailed in the Study Reference Manual.

#### **4.5 LevoCept Dosage Modification**

All subjects will receive the same LevoCept device and dosage. No Study Devices will be replaced if an expulsion or removal occurs.

#### **4.6 Concomitant Therapy**

Concomitant medications are any prescription medications or over-the-counter preparations or routine medications used by the subject taken from the time the subject signs consent shall be documented until Study Exit. Concomitant medications used as prior contraception or used to treat a prior cervical infection within 30 days of screening should also be reported. All concomitant medications, including excluded therapies, must be documented in the Concomitant Medication eCRF.

#### **4.7 LevoCept Retention Compliance**

Subjects will be instructed on how to check for study device presence by feeling for the strings in the vagina. Subjects will not be required to routinely check for study device presence, but if a subject believes the study device may have been expelled or is no longer in place, the subject can check for the study device string if desired. If the subject does not feel the strings, feels more than the strings, or has expelled the study device, the subject should be instructed to call for an urgent study visit and refrain from having sex or use appropriate non-hormonal contraception until further evaluation is completed. For detailed instructions regarding management of missing strings, refer to the Study Reference Manual.

